Secondary endpoints	
Part A:
 
 
• Pharmacokinetic profile
 
 
Part B:
 
 
• Comparison of radicular “pain now” scores as peak change from baseline and area under the curve comparing the two arms over the full six hours
 
• Comparison of Patients general impression of change between dosing arms
 
• Adverse event rates in each dosing arm
 

Exploratory endpoints	
Part A:
 
 
• Pharmacodynamic assay and/or biomarkers of LAT8881 activity.
 
 
Part B:
 
 
• Mechanical QST assessment using Von Frey Aesthesiometer
 
• Evaluate the effect of Intravenous LAT8881, compared with placebo, on VAS radicular pain scores during straight-leg raise nerve stretch
 
• Bang Binding Index assessment, whereby participant will be asked to record which dosing occasion they believe they got the active IP.
 
• Pharmacodynamic assay and/or biomarkers of LAT8881 activity.
 

Study Design	
Part A:
 
This is a double-blind, randomized, placebo-controlled, single ascending dose study within 8 healthy volunteers of intravenous administration of LAT8881 over 5 minutes.
 
Part A of the Study will enrol 8 participants, each participant has three treatment days, 1 infusion per dosing day on days 1, 4 and 7 as well as two short visits for safety blood sampling on Day 3 and 6. The 8 subjects will be split into two groups of 4 subjects each (3 IMP and 1 placebo), with the two groups dosed a few days apart.
 
Participants arrive on the morning of treatment day, receive a single infusion, leave that afternoon (no overnight stay). Participants will be dosed at staggered intervals as determined by PI. .
 
Treatments are on Days 1 (0.8 mg/kg), Day 4 (1.2 mg/kg) and Day 7 (1.8 mg/kg) or placebo to allow sufficient washout and consideration of any safety observed following each dosing day. Day 3 and 6 safety blood results must be review prior dosing on the following day.
 
Participants will fast for 8 hours pre-dose and 4 hours post dose for each dosing occasion.

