#### 4. SCHEDULE 1 OF OBSERVATIONS AND PROCEDURES PART B

Procedure	Day -30 to -2	Day 1/Day 2 (hours)															Day 9/ ETV		
	Screening	Pre Dose	Dose	5min	10 min	15 min	20 min	30 min	45 min	1	1.5	2	2.5	3	3.5	4	5	6	+/ - 1 day
Informed consent	x																		
Medical history	x																		
Inclusion/exclusion criteria	x	x																	
Demography	x																		
Physical examination, height, weight	x																		
Symptom-directed physical exam		x															x	x	
MRI or CT if >6mths 	x																		
Sciatic Pain History	x																		
3 Day NRS Pain Scores 		x																	
Pregnancy test (WOCBP) 	x	x																x	
Urine drug screen, Urinalysis and Alcohol breath test 	x	x																	
SARS-CoV-2 Test 																			
HIV, Hepatitis B & C screening	x																		
Clinical laboratory tests	x	x															x	x	
12-lead ECG	x	x										x			x		x	x	
Vital signs	x	x								x	x	x	x	x	x	x	x	x	
Spot pulse oximetry	x	x								x	x	x	x	x	x	x	x	x	
Pain scores (VAS)		x			x			x	x	x	x	x	x	x	x	x	x	x	

Provocation Assessment with VAS		x				x		x	x	x	x	x	x	x	x	x	x	x	x	x	
Patient General Impression of Change 																			x		
QST (von Frey) 		x										x				x					
Randomization		x																			
Dose administration 			x																		
AE review				x		x		x	x	x	x	x	x	x	x	x	x	x	x	x	
PK Sampling 		X		x	x		x	x	x	x									x		
PD Sampling 		x		x	x		x	x	x	x								x			
Concomitant medication review												x							x		
Bang Binding Index assessment 																		x			
Discharge 																		x			

\*# Participants who withdraw early from the study will be encouraged to return to the clinic for an ETV assessment.

\* Participants may require an unscheduled visit to address safety issues and/or for any additional PK and/or PD sample collection as required.

1 All WOCBP will have a serum pregnancy test at Screening and at the ETV visit, if applicable. Urine pregnancy tests will be performed for WOCBP at all other specified subsequent visits. If a urine pregnancy test is positive, it must be confirmed by a serum pregnancy test.

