2. Urine Drug Screen and Alcohol Breath Test will be performed in clinic. A urine dipstick will be completed at all visit. In the event of positive Leukocytes and/or nitrates that urine sample will be sent to the local labortaotry for a microscopic examination.

3. SARS-CoV-2 Test will be taken if clinically indicated and in line with local processes.

4. All participants will fast 8 hours prior and 4 hours after the study drug administration

5. Staff to contact the participant for 3 consecutive days during the week prior to dosing for documentation of daily pain scores

6. Not required if participant has current imaging available within the last 6 months

7. Mechanical Quantitative Sensory Test (QST) assessment using Von Frey Aesthesiometer will be completed by trained staff members

8. Pre-dose, 5 (mid infusion), 10 (end of infusion)  $\pm$  1 min, 20  $\pm$  1 min, 30  $\pm$  2 min, 45 min  $\pm$  5 min, 60 min  $\pm$  5 min, 6h  $\pm$  30 min from the start of the infusion of the dose.

9. Completed 6 hours post dose on Day 2 only

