#### **9.6.15. Pain assessment (VAS), Patient General Impression of Change (PGIC) and Bang Binding Index Assessment (Part B only)**

Pain Assessments will be completed using a Visual Analogue Scale (VAS). VAS scores will be collected at the timepoints in Schedule 2.

The Patient General Impression of Change will be collected at the timepoints in Schedule 2. Bang Binding Index Assessment will be collected at the timepoints in Schedule 2

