# 21. STATISTICAL ANALYSIS

## 21.1. General considerations

An analysis of Part A will be conducted when all subjects in Part A have completed Part A.

A final analysis of Part B will be conducted when all subjects have completed Part B.

The statistical analysis principles described below will be supplemented by a comprehensive statistical analysis plan (SAP) which will be finalised before the database is locked. This will contain details of methods for handling missing data and early withdrawals. Any changes to the statistical analysis plan will be described and justified in the final report.

Descriptive statistics will be used to analyse the data in both Part A and Part B of the study. The descriptive summary for the categorical variables will include counts and percentages. The descriptive summary for the continuous variables will include number of participants (n), means, medians, standard deviations, and minimum and maximum values. Pharmacokinetic measures will be analysed as for continuous variables.

In Part A and Part B, data will be tabulated and analysed with respect to subject enrolment and disposition.

In Part A, demographic, baseline characteristics and prior medications summaries will be presented overall. Concomitant medications, PD, PK and safety measure summaries will be presented by active treatment dose, placebo and overall. Note that results for the subjects on placebo across all doses will be combined for summary purposes.

---

In Part B, demographic, baseline characteristics (including history of lumbar radicular pain) and prior medications will be presented by treatment sequence and overall. Efficacy, PD, PK, concomitant medications and safety measure summaries will be presented by treatment within each treatment period and overall.

As this is a Proof-of-Concept study, no formal statistical hypotheses are being specified although some may be investigated as part of the data presentation, in which case corresponding 95% confidence intervals will be presented for treatment differences and p-values of  $<0.05$  will be declared statistically significant. Treatment comparisons will take into account the paired nature of the treatment responses where feasible and treatment period order will be ignored in any treatment comparisons.

All data will be listed for all subjects to support each table and to present all data. All statistical analyses will be performed using SAS unless otherwise stated in the SAP.

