3.2.6 Treatment groups – Part B

LAT8881 will be administered at a dose of 1.8 mg/kg via an infusion pump at a constant rate over 10 minutes.

The placebo formulation will be presented as above but without the LAT8881 active.

Tabulations for part 2 will summarise data as follows:

Demographics and baseline characteristic data, will be summarised by:

- LAT8881 1.8 mg/kg /Placebo
- Placebo/LAT8881 1.8 mg/kg
- Total

Visit based tabulations will be summarised by treatment received (LAT8881 1.8 mg/kg or Placebo) and total, and timepoint relative to within period dosing. Treatment will be assigned to individual records based on the treatment period. Timepoints will be:

- Screening (summarised as total only)
- Day 1- predose/Day 2-predose (combination of Day 1 and Day 2, summarised by treatment)
- Day 1- dose/Day 2-dose (combination of Day 1 and Day 2, summarised by treatment)
- Day 1- 5min/Day 2-5min (combination of Day 1 and Day 2, summarised by treatment)
- Day 1- 10min/Day 2-10min (combination of Day 1 and Day 2, summarised by treatment)
- Day 1- 15min/Day 2-15min (combination of Day 1 and Day 2, summarised by treatment)
- Day 1- 20min/Day 2-20min (combination of Day 1 and Day 2, summarised by treatment)
- Day 1- 30min/Day 2-30min (combination of Day 1 and Day 2, summarised by treatment)
- Day 1- 45min/Day 2-45min (combination of Day 1 and Day 2, summarised by treatment)
- Day 1- 1hr/Day 2-1hr (combination of Day 1 and Day 2, summarised by treatment)
- Day 1- 1.5hr/Day 2-1.5hr (combination of Day 1 and Day 2, summarised by treatment)
- Day 1- 2hr/Day 2-2hr (combination of Day 1 and Day 2, summarised by treatment)
- Day 1- 2.5hr/Day 2-2.5hr (combination of Day 1 and Day 2, summarised by treatment)
- Day 1- 3hr/Day 2-3hr (combination of Day 1 and Day 2, summarised by treatment)
- Day 1- 3.5hr/Day 2-3.5hr (combination of Day 1 and Day 2, summarised by treatment)
- Day 1- 4hr/Day 2-4hr (combination of Day 1 and Day 2, summarised by treatment)
- Day 1- 5hr/Day 2-5hr (combination of Day 1 and Day 2, summarised by treatment)
- Day 1- 6hr/Day 2-6hr (combination of Day 1 and Day 2, summarised by treatment)
- Day 9/ETV (summarised as total only)

○ Event based tabulations (e.g. adverse events, concomitant medications and deviations) will be summarised by treatment and total. Treatment will be assigned to individual records based on the treatment period of the start date of the event.

- Adverse Events:

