11. EFFICACY (PART B ONLY)

Analysis Set: Full Analysis Set and Per Protocol population

Parameters:

- Pain now VAS score:
 - Change from Baseline to hours 0.25, 0.5, 0.75, 1, 1.5, 2, 2.5, 3, 3.5, 4, 5 and 6,
 - Percentage change from baseline to hours 0.25, 0.5, 0.75, 1, 1.5, 2, 2.5, 3, 3.5, 4, 5 and 6
 - Peak change from baseline over 6 hours
 - Mean change from baseline over 1 to 2 hours
 - Mean change from baseline over 5 to 6 hours
- Pain on leg raise VAS score:
 - Change from Baseline to hours 0.25, 0.5, 0.75, 1, 1.5, 2, 2.5, 3, 3.5, 4, 5 and 6,
 - Percentage change from baseline to hours 0.25, 0.5, 0.75, 1, 1.5, 2, 2.5, 3, 3.5, 4, 5 and 6

- Peak change from baseline over 6 hours
 - Mean change from baseline over 1 to 2 hours
 - Mean change from baseline over 5 to 6 hours
- Patients general impression of change at hour 6 on Day 1 and on Day 2
- Mechanical QST assessment using Von Frey Aesthesiometer
- Bang Binding Index assessment at 6 hours on Day 2

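### The protocol's Part B schedule limits PGIC to Day 2 while the SAP analyses it on Day 1 and Day 2; the two must be reconciled and the ratings actually collected established

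*Protocol*

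**What the plan says.** **Protocol.**

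- The Part B schedule (section 4) has a row for "Patient General Impression of Change" marked with footnote 9, which reads "Completed 6 hours post dose on Day 2 only". The Bang index row carries the same marker.
- Section 9.6.15 adds no timing of its own: "The Patient General Impression of Change will be collected at the timepoints in Schedule 2". The section is for Part B only, so this must mean the Part B table, although that table is headed Schedule 1.
- The synopsis makes PGIC a Part B secondary endpoint: "Comparison of Patients general impression of change between dosing arms".
- Section 21.1 says "Treatment comparisons will take into account the paired nature of the treatment responses where feasible". It also asks for Part B efficacy summaries by treatment inside each period as well as overall.

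**SAP.**

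- Section 11 lists "Patients general impression of change at hour 6 on Day 1 and on Day 2" and, separately, "Bang Binding Index assessment at 6 hours on Day 2".
- Section 3.2.6 defines the six-hour timepoint for visit-based tables as "Day 1- 6hr/Day 2-6hr (combination of Day 1 and Day 2, summarised by treatment)".
- Section 11.1.1 plans three PGIC outputs: a listing by sequence and visit; counts and percentages per category for each treatment within each day and overall; and a heat map with the placebo category on one axis and the LAT8881 category on the other.
- Section 2.5, which records departures from the protocol for Part B, does not mention PGIC timing.

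**The concern.** Each participant receives one treatment per day. A rating taken on Day 2 alone therefore covers one treatment per person, and a comparison of the two treatments within a person is impossible. A site that keeps to the protocol schedule would leave the SAP's heat map with nothing to plot and the Day 1 half of its table blank.

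At stake is the within-participant comparison on a named secondary endpoint. What would remain is a comparison of different people on Day 2, after half of them had received LAT8881 the day before and half placebo. Such a comparison cannot be separated from any carry-over from Day 1. The sponsor already has this possibility in view: SAP 2.5 reports that pre-dose pain on Day 2 may have been lowered by the first day in the clinic, and adds a plot to look for a day or carry-over effect.

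**Working it through.** The plan states no sample size calculation, and therefore no figure to reproduce. The check compares the passages and then counts ratings.

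**Step 1: is the conflict in current text?** The footnote, section 9.6.15 and SAP 11 are all current, and none is a summary of changes. The protocol gives PGIC timing only through the schedule, and no protocol passage separately provides for a Day 1 rating. The SAP names Day 1 explicitly. The conflict is direct.

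**Step 2: is the marker likely to be a slip?** The Bang index asks on which occasion the participant believes active drug was given, so it makes sense only once, after the second dose. Footnote 9 fits that row, and SAP 11 agrees with it there. PGIC has the same footnote, but SAP 11 times it on both days. Without the footnote, a mark in a column block headed Day 1/Day 2 would mean both days. Protocol 21.1 also expects efficacy summaries within each period. A misplaced marker is the more natural reading, but no passage confirms it.

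**Step 3: do the documents show what was collected?** No. SAP 15 planned an interim listing and table of PGIC without naming the day. SAP 2.5 confirms only that the planned graphical outputs were produced. SAP 17 cites an annotated study file that is not part of the documents.

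**Step 4: count ratings under each possibility.** Inputs: 17 expected completers and 14 completers at the interim (both SAP 2.5); one rating per rated day; a pair needs both days. At most 17 − 14 = 3 participants could benefit from a correction made after the interim.

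| | Both days rated | Day 2 only throughout | Day 2 only for 14, both days for 3 |
|---|---|---|---|
| Ratings | 2 × 17 = 34 | 17 | 14 + 2 × 3 = 20 |
| Heat-map pairs | 17 | 0 | 3 |
| Day 1 ratings | 17 | 0 | 3 |

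The table has 2 treatments × 2 days = 4 treatment-by-day cells. Under Day 2 only, the 2 Day 1 cells are empty and the overall columns simply repeat Day 2. The overall comparison falls from 17 against 17 (the same people) to about 9 against 8 (different people). The 9/8 split is an assumption, because the documents give only the planned 10 and 10.

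At the planned maximum of 20, the same count gives 40 ratings and 20 pairs with both days, or 20 ratings and 0 pairs with Day 2 only.

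All these counts are for completers with complete data. The per-protocol set may be smaller: SAP 2.5 reports two participants who received an estimated 60–65% of the dose, and SAP 4.1.2 allows exclusion for inadequate exposure. The full analysis set is everyone randomised and may be larger.

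**The case against.** The best counter-argument is that the harm is conditional and the documents lean against it. Protocol 21.1 expects within-period efficacy summaries. SAP 11 deliberately times PGIC and the Bang index differently. The SAP was revised after the interim outputs were reviewed and still plans the heat map. This stands as far as it goes: a stray marker is the likelier explanation. It is not evidence of collection, because the interim PGIC outputs are planned in SAP 15 but not confirmed.

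It can also be said that pairing in Protocol 21.1 is required only where feasible, so an unpaired PGIC summary would not breach it, and that PGIC is descriptive in a proof-of-concept study with no formal hypotheses. Both points stand. They lower the weight of the matter but do not resolve the conflict, because the SAP itself commits to an output that needs both ratings.

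A reader might go further and put a number on the carry-over bias in a Day 2 comparison, or on the precision lost by not pairing. The documents do not support this. PGIC is a seven-category rating, and the SAP plans no model, contrast or test for it. Such figures would need an additive numeric score, and the documents do not say what point in time the change is judged against. Only the qualitative statement holds: an unpaired Day 2 comparison cannot be separated from any carry-over.

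**Conclusion.** The contradiction is certain; the loss of data is not. A reader might infer that Day 1 PGIC is missing and that the planned analysis has failed. The documents do not show that, and the indirect signs point the other way.

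If footnote 9 was followed, 17 of 34 ratings and all 17 heat-map pairs are absent among expected completers, both Day 1 cells are empty, and an unpaired Day 2 comparison between sequences is all that remains. If Day 1 was rated, nothing is lost, and the error is confined to the protocol schedule and to the missing entry in SAP 2.5. The size rests on 17 completers with complete data; per-protocol and full-analysis-set counts may differ. The primary endpoint is not affected.

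This should be fixed: it concerns a named secondary endpoint, and either Day 1 ratings were taken outside the written schedule or a planned output cannot be produced. Either case needs a record.

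**What to change.** 1. Check the CRF, and the interim PGIC listing if it was produced, to establish on which days PGIC was recorded. The annotated file cited in SAP 17 is a place to start.
2. If anyone remains to be dosed, take footnote 9 off the PGIC row so that PGIC is rated at 6 hours on both days, by approved amendment where Protocol 22.4 and 22.5 require it. If nobody remains, record the discrepancy in the final report instead.
3. If Day 1 ratings exist, keep the SAP analysis. If they do not, restrict the heat map to participants with both ratings, or drop it if there are none. Then report PGIC as an unpaired Day 2 comparison, stating that it cannot be separated from any carry-over.
4. Record the outcome in SAP 2.5.

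**Cost.** One check of existing records and one SAP entry. Any schedule change may need ethics committee approval and would add one rating on Day 1 for at most 3 participants. SAP 2.5 recommends closing the study on 12 May 2023, and the documents do not show whether anyone was still undosed, so step 2 may reduce to a note in the report. No change can recover Day 1 ratings for the 14 who had completed by the interim if they were not taken.

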## 5. INTRODUCTION

### 5.1. Background

#### **Neuropathic pain**

Neuropathic pain (NP) is defined as pain caused by a lesion or disease of the somatosensory nervous system. The damage may be located either centrally or peripherally. Examples of central neuropathic pain include pain in Multiple Sclerosis or Parkinson's disease and pain after a stroke; examples of peripheral neuropathic pain include painful diabetic neuropathy, phantom limb pain, post-herpetic neuralgia, chemotherapy induced polyneuropathy, and trigeminal neuralgia.

The symptoms of peripheral neuropathic pain vary, depending upon the type of nerves that are damaged. Typical descriptions of the pain include shooting, stabbing, electric shock, burning, tingling, tight, numbness, prickling, itching and a sensation of pins and needles. Symptoms may also include allodynia, hyperalgesia, anaesthesia dolorosa, with sensory gain or loss. The impact of neuropathic pain on both the individual and on society is substantial. In addition to the morbidity associated with the pain itself, patients with neuropathic pain have a decreased quality of life, increased use of healthcare resources, increased absenteeism and decreased productivity at work.

The development of validated questionnaires for neuropathic pain has enabled better assessment of its prevalence in the general population. A recent systematic review of epidemiological studies of neuropathic pain estimated that the prevalence of pain with neuropathic characteristics ranged from 7- 10%. This is likely to increase as the population ages, when there will be an increased incidence of risk factors for neuropathic pain, such as diabetes, cancer and cancer chemotherapy.

The treatment of neuropathic pain is challenging as it is generally not possible to alleviate the cause of the pain. Rather, therapy focuses on treating the symptoms. Non-pharmacological treatments, such as physical exercise, cognitive behavioural therapy and meditation have been proposed but there is only weak evidence for the efficacy of such approaches. Pharmacological therapy is the mainstay of treatment. A recent review of 229 randomised double-blind studies of oral and topical pharmacotherapy for neuropathic pain by the Neuropathic Pain Special Interest Group (NeuPSIG) of the International Association for the Study of Pain (IASP) recommended gabapentin, gabapentin extended release/enacarbil, pregabalin, duloxetine, venlafaxine and tricyclic antidepressants as first line therapy. However, it was found that outcomes with these agents were generally only modest, with 4 to 10 patients requiring active treatment for a 50% reduction in pain, compared with placebo treatment. Moreover, many of these therapies have side effects, such as somnolence, dizziness, motor imbalance and cognitive impairment, which restrict a patient's activities and diminish their quality of life.

There is clearly an unmet need for more effective therapies to treat neuropathic pain. LAT8881 has a different mechanism of action to current therapies and has shown promising activity in animal models of neuropathic pain. It also has a good pre-clinical and clinical

---

safety record. This is the first clinical study to investigate this compound (by intravenous dosing) in neuropathic pain.

### LAT8881

LAT8881 (Tyr-hGH177-191) is a 16 amino acid peptide fragment based on the C-terminus of human-growth hormone (hGH177-191) with an additional tyrosine at the N-terminus. It was initially developed for the treatment of obesity, (known during that time as AOD9604), but Phase 2 clinical studies did not show a statistically significant weight loss in obese subjects and development for this indication was discontinued.

Subsequent to these clinical trials in obesity, LAT8881 was successfully investigated in a variety of animal models of neuropathic pain:

- An analgesic effect was demonstrated in a number of *in vivo* preclinical studies after administration of LAT8881 at doses ranging from 1.0 to 10 mg/kg, including when administered intravenously, orally and subcutaneously .
- *In vitro* electrophysiological studies suggested that LAT8881 inhibits neuronal activity in a manner consistent with a reduction in pain signalling.
- Mechanism of action studies identified the target of LAT8881 to be LANCL1, an inner cell-membrane hub protein ubiquitously expressed but high in the nervous system, respiratory tissue, and testis, known to be involved in protection from cell stressors by engaging several pathways (such as AKT/mTORC, Eps8, GSH, and deubiquitination) but, until now, not known as a potential therapeutic target for the treatment of neuropathic pain.

The proposed repurposing of LAT8881 as a treatment for neuropathic pain via a novel and unique mechanism is underpinned by the preclinical and clinical safety data obtained when it was investigated as an obesity treatment, as detailed in the study Investigational brochure.

